## 8.7 Additional Endpoints

Summary statistics will be provided for the following:

- Procedure duration: defined as the difference between “When was the patient’s percutaneous wound closed?” from the Mini-PCNL eCRF and “When is the Cystoscope introduced?” from the Pre-Procedure Setup eCRF
- Cumulative stone burden at the 30-day follow-up visit as well as change in stone burden from the Screening/Baseline visit; Change in cumulative stone burden (%) will also be summarized and is defined as  $100 \times (\text{Change}/\text{Baseline})$ . Similar analyses will be presented for cumulative stone volume at the 30-day follow-up visit.
- Efficiency of stone ablation defined as pre-operative stone volume divided by lithotripsy time. Lithotripsy time is defined as the difference between the treatment complete time from the mini-PCNL eCRF and first lithotripsy start time on the Laser Settings eCRF.
- Placement of a stent or nephrostomy tube as well as duration of stent placement in days: defined as the difference between “Date of stent extraction” from the Physical Exam and Vital Signs eCRF at the 30-day visit and “Did you place a ureteral stent in this patient?” from the Mini-PCNL eCRF + 1
- Subject weight post-procedure as well as change from pre-procedure weight
- Length of stay in nights: defined as “Date of hospital discharge” – “Date of hospital admission”
- Selected labs taken immediately post procedure (sodium, creatinine, hematocrit) as well as change from the Screening/Baseline visit
- Total fluoroscopy dosage (mGy) and time (minutes)
- Percutaneous access fluoroscopy dosage (mGy) and time (minutes)

- Wisconsin Stone Quality of Life survey over time as well as change from baseline (overall score and individual domains of social impact, emotional impact, disease impact and vitality impact)
- PROMIS-29 Profile v2.1 survey over time as well as change from baseline (overall score and individual domains of physical function, anxiety, depression, fatigue, sleep disturbance, social role satisfaction, and pain interference).

Counts and percentages will be provided for the following:

- Number and location of post-operative stones at the Day 1 and Day 30 follow-up visits.
- Number of needle attempts
- Need to relocate stones
- Number of Randall's plaques in each of the Upper Pole, Interpole, and Lower Pole as reported in the Investigator Assessment eCRF
- Subjects requiring retreatment for stone removal within the duration of the study, as reported within the Concomitant Procedure eCRF
- Responses to the Investigator Experience surveys regarding the procedure, retrograde instruments, antegrade instruments/controller, and user experience.

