In this study, the effectiveness of MONARCH™ in treating stones will be assessed from the post-operative Day 30 stone free rate, where stone free is defined as CT assessment showing  $\leq 4$  mm residual fragments. Subjects will undergo a mini-PCNL procedure with the MONARCH™ system. As an exploratory assessment of immediate post-operative stone clearance, the presence of any residual stones will be initially assessed by CT within 1 day of the procedure. Subsequently, subjects will undergo CT assessment 30-days post-procedure to measure the effectiveness of the procedure. However, to minimize radiation exposure, subjects without any residual fragments observed by CT at post-operative Day 1 will not undergo the additional CT at post-operative Day 30. Rather, these subjects will be presumed to be stone free at Day 30.

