Blood tests including the PT/INR coagulation test. These tests may be needed before the procedure to ensure that study patients have no problems related to blood clotting. Bleeding can sometimes occur after percutaneous renal procedures. The study patients will be asked to stop anticoagulants several days prior to the procedure.

The electronic version of this document is stored in Agile PLM and is considered the controlled copy.

Printed copies are for reference only and considered UNCONTROLLED.

CONFIDENTIAL AND PROPRIETARY OF AURIS HEALTH, INC.

	PROTOCOL	Doc #:	104-016667-00
	Monarch Uro - Post-Operative Outcomes Study (2023-URO-0001)	Rev:	C
		Page:	20 of 52

Preoperative Imaging: De-identified scans will be provided to the study Sponsor.

CT-KUB non contrast: Pre-op CT-KUB non contrast will be performed as part of the screening assessment, up to 120 days prior to the procedure.

Postoperative Follow-up Imaging: De-identified scans will be provided to the study Sponsor.

CT-KUB non-contrast: All patients will receive to determine remaining stone burden at Day 1. Patients with residual stones will have an additional CT-KUB non-contrast at Day 30. The secondary endpoint, stone free rate at Day 30, is the percentage of patients who are stone free assessed by CT, where stone free is defined as having  $\leq 4$  mm residual stones.

Fluoroscopy: Fluoroscopy will be used provide an additional viewing method during the procedure. De-identified images will be provided to the study Sponsor.

Endoscopy: Endoscopic ureteroscopy will be used to evaluate the presence of residual stone fragments in the kidney at the end of the procedure. Assessment will be recorded on CRFs.

Concomitant Medications. All medications beginning from 30-days prior to screening until subject exit will be recorded on a rolling medication log on the relevant case report forms.

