## 8.6 Secondary Endpoints and Associated Hypotheses

The following secondary endpoints are specified for this study:

- Stone free rate ( $\leq 4$  mm residual fragments, measured 30-days post-operative)
- Adverse events through 90-days post-operative, scored on the Clavien-Dindo scale
- Conversion to conventional treatment methods due to study device-related safety event

No associated hypotheses are specified.

The stone free rate will be computed as the percentage of patients who are stone free assessed by computed-tomography (CT) scan at post-operative Day 30. Stone free is defined as having  $\leq 4$  mm residual cumulative stone burden detected by CT. Patients who are found to not have any residual stone fragments at Day 1, will not undergo a second CT at post-operative Day 30, and will be presumed to be stone free at Day 30 for this calculation. The number and percentage of procedures resulting in a subject who is determined to be stone free at Day 30 will be

summarized and a 95% confidence interval will be estimated. Similar analyses will be performed for the stone-free rate at Day 1.

All adverse events will be captured up to post-operative Day 90, at which point the subject exits the study. Summaries will be provided for all adverse events by MedDRA System Organ Class and Preferred Term. Similar summaries will be provided for device-related AEs, procedure-related AEs, serious adverse events (SAEs), device-related SAEs, and procedure-related SAEs. Adverse events will also be scored on the Clavien-Dindo scale and summaries will be provided by System Organ Class and Preferred Term for events that are graded at III or higher on the Clavien-Dindo scale and then similarly for those that are Grade II or lower in a separate output table.

The number and percentage of procedures converted to conventional stone removal procedures (e.g., ureteroscopy or percutaneous nephrolithotomy) due to the occurrence of a study device-related safety event will be summarized. A qualifying safety event is a study device-related adverse event that occurs during the study procedure that prompts the physician to abort the study procedure and pursue a conventional stone removal procedure.

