## 8.10 Handling of Missing Data

All summaries will be performed only on subjects undergoing the scheduled procedure and only observed data will be summarized. There will be no imputation of data for early terminated subjects or for missing data within the database.

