#### 8.15 Exploratory Analyses

Counts and percentages (labeled as the “stone free rate”) will be provided for the number of procedures where post-operative cumulative stone burden is in the following categories: 0 mm,  $\leq 2$  mm, and  $\leq 4$ mm. Analyses of the following cohorts will be performed:

- All subjects receiving the study procedure
- Pre-operative stone burden (1-2 cm), representing “intermediate-sized stones”
- Pre-operative stone burden (1-3 cm), representing “classic mini-PCNL stones”
- Pre-operative stone burden (1-4 cm), representing “targeted patient pool”
- Pre-operative stone burden ( $> 2$  cm), representing “classic PCNL stones”
- Pre-operative stone burden ( $> 4$  cm), representing “very large-sized stone”

Summary statistics will be presented for the total volume of fluid input from the MONARCH™ fluidics pump and total volume of fluid collected in the waste management system.

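### As written, SAP 8.7's Day-30 stone burden, volume and percent change can cover only patients who still had stones on Day 1

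*SAP*

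**What the plan says.** **Who is scanned at Day 30.** Every patient is to have a CT on Day 1. After that, "Patients with residual stones will have an additional CT-KUB non-contrast at Day 30" (Protocol 3.2, Assessment schedule), while "subjects without any residual fragments observed by CT at post-operative Day 1 will not undergo the additional CT at post-operative Day 30" (Protocol 2.1). Table 1 of the protocol accordingly marks the Day-30 CT as done only where needed.

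**What is summarised at Day 30.** SAP 8.7 lists "Cumulative stone burden at the 30-day follow-up visit as well as change in stone burden from the Screening/Baseline visit", defines percent change as 100 × (change/baseline), and adds: "Similar analyses will be presented for cumulative stone volume at the 30-day follow-up visit". It also asks for the number and location of stones at Day 1 and Day 30. It gives no value or rule for a patient who, by design, has no Day-30 scan.

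**What is said about cleared patients.** In SAP 8.6 they "will not undergo a second CT at post-operative Day 30, and will be presumed to be stone free at Day 30 for this calculation". The calculation meant there is the stone-free rate, with stone free defined as at most 4 mm.

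**What is said about absent values.** SAP 8.10 restricts all summaries to observed data and states: "There will be no imputation of data for early terminated subjects or for missing data within the database". SAP 4 rules out assigning an observation to any visit other than the one under which it was entered. SAP 8.12 plans no sensitivity analysis. SAP 6 places all performance endpoints on the Full Analysis Set.

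**The concern.** Absence of a Day-30 scan is planned, and it is determined by outcome: a patient has no Day-30 measurement because the Day-1 CT showed no stone. A summary of Day-30 measurements therefore describes only those patients in whom clearance was incomplete on Day 1, although it is meant for the Full Analysis Set.

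Two things follow. Mean remaining burden and volume are overstated, and percent reduction understated, relative to all treated patients. And two Day-30 effectiveness results, the stone-free rate and the change in burden, rest on different denominators with nothing in the SAP to say so. A reader who sets them side by side would take them to describe the same patients. The burden summary also cannot register complete immediate clearance, which the protocol's introduction names as a possible advantage of the device that the study will explore.

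**Working it through.** The plan states no expected clearance rate, residual burden or powered sample size, so there is no figure of its own to reproduce. The check has two parts.

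**1. Is there any written route to a Day-30 value for a cleared patient?**

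| Possible route | What the text allows |
|---|---|
| Measure it | No: the Day-30 CT is omitted by design (Protocol 2.1, 3.2; SAP 8.6) |
| Use the SAP 8.6 presumption | Limited to the stone-free rate; and it gives at most 4 mm, not a burden of 0 mm |
| Impute it | Barred by SAP 8.10 |
| Carry the Day-1 zero forward | Barred by SAP 4 |

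No route remains, so the rules read together leave only patients scanned at Day 30 in these summaries.

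**2. How large could the effect be?** Let *p* be the share clear on Day 1. Assume that all other patients are scanned at Day 30 and that cleared patients stay at zero.

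*Percent reduction.* Let *R* be the mean percent reduction among scanned patients. The table shows *R*; all treated patients have 100*p* + (1 − *p*)*R*.

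- *p* = 0.6, *R* = 80 (assumed): 60 + 0.4 × 80 = 92, against 80 in the table.
- *p* = 0.8, *R* = 80 (assumed): 80 + 0.2 × 80 = 96, against 80 in the table.

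*Burden.* Assume a baseline *B* = 20 mm in everyone and a Day-30 mean *r* = 5 mm among scanned patients. N = 60 is the planned maximum; SAP 1.2 says enrolment stopped earlier, and the final number is not given. Scanned only: 5.0 mm and 100 × (5 − 20)/20 = −75.0%, whatever *p* is. All treated: (1 − *p*)*r* and 100 × ((1 − *p*)*r* − *B*)/*B*.

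| Clear on Day 1 | Scanned | Mean burden, all treated | Percent change, all treated | Percent change, scanned only |
|---|---|---|---|---|
| 30% | 42 of 60 | 3.5 mm | −82.5% | −75.0% |
| 50% | 30 of 60 | 2.5 mm | −87.5% | −75.0% |
| 70% | 18 of 60 | 1.5 mm | −92.5% | −75.0% |
| 80% | 12 of 60 | 1.0 mm | −95.0% | −75.0% |

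The gap in percentage points is 100 × *p* × *r*/*B*. It runs from 100 × 0.3 × 3/20 = 4.5 (*r* = 3 mm, 30% clear) to 100 × 0.8 × 8/20 = 32 (*r* = 8 mm, 80% clear).

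**The case against.** **The restriction is inferred.** No sentence in the SAP defines this subset. Protocol 2.1 presumes cleared patients stone free at Day 30 without limiting the presumption to one calculation, and the SAP authors evidently saw no conflict between the SAP 8.6 presumption and the ban on imputation. A programmer might enter 0 mm, or the Day-30 eCRF might accept a zero without a scan; that form cannot be seen. This stands as far as it goes: what will actually be run is not known. But nothing written permits the zero outside the stone-free rate, and SAP 8.10 and SAP 4 both point the other way.

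**The reduced set would be visible, and it is not simply the failures.** SAP 8.1 requires the number of observations in each continuous summary and a listing of all eCRF data. Change is paired within patient, so each scanned patient is still compared with his or her own baseline. The scanned group also includes patients with 4 mm or less, who count as stone free. All of this is fair. A visible n shows that patients are absent; it does not say that they are the fully cleared ones.

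**A reader might extend the point to SAP 8.15.** Its 0, 2 and 4 mm categories concern the "number of procedures where post-operative cumulative stone burden is in the following categories" and name no visit. On an assumed 60% clear on Day 1 and 20–30% of the rest clear later, an observed-only 0 mm rate at Day 30 would be 20–30%, against 60 + 0.4 × 20 = 68% to 60 + 0.4 × 30 = 72% for all patients. The documents do not support that as a forced result. Protocol 3.1 sets these thresholds up as sub-analyses of the stone-free rate at Day 1 and Day 30, and SAP 8.15 labels them as that rate, so the SAP 8.6 presumption can reasonably be read as covering them. What remains is an ambiguity: presumed stone free means at most 4 mm, which does not by itself place a patient in the 0 or 2 mm category.

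**The endpoints are minor.** They are additional and descriptive, in a single-arm study without hypotheses, and the distortion works against the device. This bears on severity and is accepted.

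**Conclusion.** The point holds for SAP 8.7. Under the rules as written, Day-30 burden, volume, change, percent change and stone counts can be summarised only in patients scanned at Day 30, who by design had residual stones on Day 1. Provided cleared patients are in truth at zero on Day 30 and the scanned patients retain some stone on average, the direction is certain: remaining burden too high, reduction too low. The size is not known, because every clearance rate and residual burden used above is an assumption; over the range examined the gap is 4.5 to 32 percentage points.

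A reader might infer that the trial's main results are affected. They are not. The primary endpoint does not use the Day-30 CT, and the 4 mm stone-free rate has its own rule for cleared patients. For SAP 8.15 the finding is a need for clarification, not a demonstrated error. Severity: should-fix.

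**What to change.** 1. **SAP 8.7.** State that procedures with no residual fragments on the Day-1 CT are counted at Day 30 as 0 mm burden, zero volume and zero stones (change −100%), carried forward from the Day-1 CT. Do not present this as the SAP 8.6 presumption, which gives only at most 4 mm. Report how many procedures were so assigned. Show the scanned-only result beside it, labelled as limited to patients with residual stones on Day 1.
2. **SAP 8.10 and SAP 4.** Add a matching exception to each. Without the one in SAP 4, the new rule would contradict the ban on moving observations between visits.
3. **SAP 8.15.** Repeat the Day 1 and Day 30 visits from Protocol 3.1, and state that the same rule places these patients in the 0 mm category at Day 30.

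The cost is a few sentences across four SAP sections, made as an amendment because SAP 8.1 requires one when a described approach is altered. No new data or scans are needed. The text should be settled before the tables are programmed.

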 All medications beginning from 30-days prior to screening until subject exit will be recorded on a rolling log

Informed Consent. A study specific, IRB approved written informed consent must be obtained for all patients who are potential study candidates before any study-specific tests or procedures are performed.

Pregnancy Test (if applicable). If there is the potential for pregnancy, a serum pregnancy test will be conducted before entry into the study.

Preliminary qualification (Investigator/Staff). Sponsor or its designee will train the Principal Investigator and sub-investigators and research staff in the proper use of the investigational products and Protocol requirements prior to the onset of subject enrollment into the investigation or trial. The Principal Investigator is responsible for certifying that key personnel have received adequate training to ensure they are aware of the regulations governing human subjects research and understand and adhere to the Institutional Review Board- (IRB)-approved research protocol. Compliance with these standards provides assurance that the rights, safety, and well-being of human subjects are protected, and the integrity of the data collected.

Inclusion/Exclusion criteria. Potential study candidates must meet the study specific Inclusion/Exclusion criteria based on the screening assessment. For the purpose of this study, a kidney stone is defined as calculi located within the renal portion of the collecting system as opposed to ureter or bladder.

Medical history. During the screening/baseline assessment, the investigator or coordinator will record details of medical history as they relate to urologic status.

Physical examination. The investigator will perform a brief, directed physical examination, and document any preoperative abnormalities. The examination will be repeated at discharge and 30 days post-procedure.

BMP (Basic Metabolic Panel) and selected metabolics. This involves a sample of blood drawn (1-3 cxc) to perform standard hematology and biochemistry

Urinalysis and Culture. A urine specimen will be analyzed for infection.

Renal Ultrasound Scan. Ultrasound examination of the kidneys postoperatively to detect stones obstruction and/or fluid collection.

Electrocardiogram (ECG). Stickers will be placed on each arm and leg and the chest area and a heart tracing is performed to measure electrical activity of the heart.

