### 8.1 Interval Windows

Interval windows for the purpose of analysis in this study will not be defined outside of those already specified in the protocol for visit scheduling. The final visit occurs approximately 90 days after surgery, thus no interval windows need to be defined given the absence of long-term follow-up in this study. The Schedule of Assessments specifies a window of 7 days around the scheduling of the 30-day follow-up visit, and any information entered in the eCRFs at this visit will correspond to the 30-day visit. The Schedule of Assessments specifies a window of 14 days around the scheduling of the 90-day follow-up visit, and any information entered in the eCRFs at this visit will correspond to the 90-day visit. There will be no assigning of observations to time points outside of the visit to which they are recorded in the eCRFs.

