# 4 Interval Windows

Interval windows for the purpose of analysis in this study are not defined outside of those already specified in the protocol for visit scheduling where the collection of data for the primary and safety endpoints occurs.

Table 1 Schedule of Assessments in the protocol specifies the following visits and windows where applicable:

- Screening/baseline: completed not more than 120 days prior to the procedure
- Procedure Day
- Follow-Up, Day 1
- Post-operative 30-day follow-up ( $\pm$  7 days)

- Post-operative 90-day follow-up ( $\pm$  14 days)

Any information entered in the electronic Case Report Forms (eCRFs) at a given visit will correspond to the scheduled visit. There will be no assigning of observations to time points outside of the visit to which they are recorded in the eCRFs.

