## 8 Statistical Analysis Methods

### 8.1 General Conventions

Subject data will be summarized in tables and presented in further detail in listings. All eCRF data will be listed per subject for all subjects. Descriptive statistical analyses will be provided for pre-specified study endpoints. Summaries for continuous variables will include a minimum of number of observations (n), mean, standard deviation, median, minimum, and maximum. Summaries for categorical variables will include number and percentage.

Analyses will be conducted using SAS software. During the course of programming of tables for summaries that are described in this SAP, minor modifications may become necessary. Examples of these minor modifications include, but are not limited to, re-wording of a footnote, addition of a footnote, re-labeling of a column, or addition or removal of a column from a listing. In cases where modifications to tables or listings are not related to a change in statistical analysis methodology or conclusions that could be made on the originally proposed

methodology, then no amendment of the SAP is necessary. Changes to planned analyses specified in the protocol or alterations of an approach that is described herein, will require an amendment to the SAP.

Baseline for all parameters will be defined as the last available measurement on or before the procedure date.

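### Stent duration uses only the extraction date on the 30-day form, so any stent still in place at that visit and not dated there later is dropped because its duration is long

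*SAP*

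**What the plan says.** SAP 8.7 (Additional Endpoints) lists stent placement and the duration of stenting in days. The duration is a difference of two eCRF items plus 1.

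- **End:** the stent extraction date, taken "from the Physical Exam and Vital Signs eCRF at the 30-day visit". No other form is named.
- **Start:** the Mini-PCNL item "Did you place a ureteral stent in this patient". No placement or procedure date is named.

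Four other provisions bear on what happens to a late removal.

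- Protocol 8.1: "The Schedule of Assessments specifies a window of 7 days around the scheduling of the 30-day follow-up visit".
- Protocol 3.2, on the physical examination: "The examination will be repeated at discharge and 30 days post-procedure". Table 1 schedules no physical examination at Day 90.
- SAP 4: "There will be no assigning of observations to time points outside of the visit to which they are recorded in the eCRFs".
- SAP 8.10: "only observed data will be summarized", and "There will be no imputation of data for early terminated subjects or for missing data within the database".

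The SAP has no rule for a stent that is still in place at the 30-day visit.

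**The concern.** A stent that is in place when the 30-day form is completed has no extraction date to record. Under the stated definition it then has no duration, and the observed-data rule removes it from the summary. It is removed because its duration is long, so the loss depends on the outcome itself and the remaining values would be too short on average.

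The case is not far-fetched. Protocol 7.1 includes a forgotten stent among the known procedure-related events, and follow-up runs to Day 90. At stake is whether the summary describes all stents placed or only those removed by about one month, without saying which.

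The start term is a separate and smaller matter. A date minus the answer to a yes/no question cannot be computed as written.

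**Working it through.** The plan states no figure for stent duration, so there is none to reproduce.

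**Step 1: the cut-off.** The visit is at Day 30 ± 7, so 30 - 7 = 23 and 30 + 7 = 37. Unless the form is completed later, the latest removal it can hold falls between Day 23 and Day 37, depending on when that subject was seen.

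**Step 2: later capture.** The definition provides none. No physical examination is scheduled after the 30-day visit, observations are not moved between visits, and nothing is imputed.

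**Step 3: effect on the mean.** Let p be the share of stents removed after the subject's 30-day visit, E the mean duration of those removed by the visit, and L the mean of those removed later.

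- True mean = (1 - p) × E + p × L
- Reported mean = E
- Reported minus true = -p × (L - E)

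The "+ 1" in the definition cancels in this difference. None of p, E and L is in the documents, so all values below are assumptions. The middle column uses E = 14 and L = 45, so L - E = 31. The last column spans E from 7 to 21 and L from 38 to 60, so L - E runs from 38 - 21 = 17 to 60 - 7 = 53.

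| p | Shift, E = 14 and L = 45 (days) | Shift over the assumed range (days) |
|---|---|---|
| 0% | 0 | 0 |
| 2% | -0.6 | -0.3 to -1.1 |
| 5% | -1.6 | -0.9 to -2.7 |
| 10% | -3.1 | -1.7 to -5.3 |
| 20% | -6.2 | -3.4 to -10.6 |

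**Step 4: in counts.** With 60 stented subjects, the original enrollment ceiling, one late stent shifts the mean by 31/60 = 0.5 day, three by 1.6 days and six by 3.1 days. Enrollment stopped short of 60 and the final number is not given. With 30 stented subjects (assumed), one late stent shifts it by 31/30 = 1.0 day.

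**Step 5: a distributional check.** Dwell times were simulated as lognormal (log-SD 0.4 and 0.6, assumed), with the visit day uniform on 23 to 37. A duration counted only if removal was on or before the visit.

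| Median dwell assumed (days) | Still in place at visit | Shift in mean (days) | Shift in median (days) |
|---|---|---|---|
| 7 | 0% to 1% | -0.01 to -0.25 | 0 to -0.05 |
| 14 | 4% to 11% | -0.7 to -2.9 | -0.3 to -1.1 |
| 21 | 21% to 29% | -3.5 to -7.8 | -2.1 to -4.2 |

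The answer therefore turns on how long stents are usually left in, which the documents do not say. With short dwell times the effect is negligible. In these runs the median moves less than the mean.

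**The case against.** The strongest reply is that no bias has been shown. The documents give no dwell time, no removal schedule and no share removed late; if every stent is out by the 30-day visit, the shift is exactly zero. This stands, and the point is conditional for that reason.

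Second, the eCRF is not supplied. The extraction-date field may be completed after the visit or following a query, and the rule against reassigning observations does not forbid that. The placement item may also carry a linked date. Neither can be excluded. A reader might infer that the reported maximum can never exceed 37 days. The documents do not support this, because late entry is possible and the "+ 1" turns a Day 37 removal into 38 days.

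Third, the start term is only a drafting slip. The item sits on the procedure form, a programmer would use the procedure date, and no bias follows. This also stands.

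Fourth, the loss need not be silent. SAP 8.1 states: "Summaries for continuous variables will include a minimum of number of observations (n), mean, standard deviation, median, minimum, and maximum". A reader could set that n against the count of stents placed, and SAP 8.8 lists concomitant procedures. That would reveal a gap but would not correct the mean, median or maximum, and it relies on the reader making the comparison.

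Fifth, a Kaplan-Meier summary may seem heavy for a descriptive item in at most 60 subjects. It is needed only if some stents lack a removal date.

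What survives is that the stated rule gives a wrong summary whenever a removal is late and not back-entered, and the SAP does not say how to handle that case.

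**Conclusion.** The concern holds in conditional form. If any stent is still in place at the 30-day visit and its date is not added to that form later, its duration is dropped because it is long, and the reported mean, median and maximum would be too low. With assumed means of 14 and 45 days the mean would be short by about 1.6 days at 5% late and 3.1 days at 10% late; with none late there is no error.

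A reader might go further and infer that the mean is biased short, or quote a large percentage understatement. The documents do not support either. Any such figure rests wholly on assumed dwell times and late shares, and a fair range starts at zero. Nor do they show that stent dates are captured through Day 90: no physical examination is scheduled then, and SAP 8.7 cites the Concomitant Procedure eCRF only for retreatment.

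Severity is minor. Stent duration is a descriptive additional endpoint, is not among the derived endpoints in Protocol 3.1, and affects no primary or secondary endpoint.

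**What to change.** Amend the stent item in SAP 8.7 as follows.

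1. Define duration as extraction date minus procedure date, and state whether the "+ 1" is kept.
2. Take the extraction date from any eCRF record through study exit where one exists: the 30-day form, the Concomitant Procedure eCRF or an unscheduled visit.
3. Report the number of stents placed, the number with an extraction date, and the number still in place at the 30-day visit and at study exit.
4. If any stent is still in place or undated, censor it at the last contact at which it was known to be in place, and report the Kaplan-Meier median instead of an observed-only mean.

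The cost is a few lines of SAP text and code, with no new visit or assessment. SAP 8.1 already requires an amendment when a described approach is altered, and correcting the start term calls for an edit to this item in any case. If no removal is late, the result is essentially unchanged. Before the edit, check on the eCRF whether the extraction field can be completed after the visit and whether later removals are recorded anywhere; if they are not, the counts in item 3 and the censoring in item 4 are the most that the data allow.
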